The primary outcome analysis is an ITT analysis of the categorization of the level of cortical bridging seen on focus CT at 3-months. The operational definition of cortical bridging is a five-level ordinal scale from "not healed" to "healed" (cf. protocol) adjudicated by the radiologists and clinicians, with two qualifications: 1) if endpoint assessment is missing because of a drop-out or loss-to-follow subsequent to an AE or SAE, the endpoint will be coded as "not healed"; 2) if the endpoint is missing for any other reason, the endpoint will be coded as the last available coding of the focus CT assessment. The treatment difference in cortical bridging will be evaluated by a 2x5 chi-square (group x score) with a trend test (Jonckheere-Terpstra) for the ordinal

level of bridging to see whether the TPTD treated participants “trend” to have a greater proportion of higher bridging scores than the placebo group.

Secondary analysis of the treatment group differences in the change in fracture healing scores across the 3-months of the placebo-controlled phase will use a generalized estimating equation for longitudinal repeated measures assuming a Poisson distribution with observation-level weighting from a logistic regression analysis of the missingness pattern following the approach used by Fitzmaurice, Lair and Ware (2011). The outcome will be coded as described for the primary outcome ITT analysis. Missing covariate values will be filled using the fully conditional specification multiple imputation method to impute a monotonically missing data pattern: outcomes will not be imputed. Continuous covariates will use the predictive mean matching method while classification covariates will use a logistic regression method.

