**Screening visit:** At the screening visit, a Mini Mental Status Exam (MMSE) will be given to be sure that the patient is capable of providing informed consent and of completing the trial. Any persons with moderate or severe cognitive impairment will be excluded (score  $\leq$ 18 of 30 points). The consent form will be reviewed and signed. A comprehensive assessment of medical history and a brief physical exam will be performed. Blood samples will be obtained and levels of creatinine, alkaline phosphatase, calcium, intact-parathyroid hormone, and 25(OH)D will be measured. Pelvic radiographs and a full CT scan will be reviewed or obtained to determine if fractures are: single rami, multiple rami fractures or sacral and pelvic fractures (healing of sacral fractures will not be assessed, although the existence of a sacral fracture with a pubic rami fracture will not exclude an individual). In addition, the fracture will be classified by amount of displacement/overriding with 3 categories: Minimal/No displacement, Mild displacement, Moderate displacement. A loading dose of vitamin D (50,000 IU) will be given in order to normalize vitamin D in this population with high prevalence of vitamin D deficiency before initiating treatment (goal within 2 weeks of the fracture). Serum calcium must be below or equal to normal for the lab. Calcium supplements or dietary modifications will be recommended as needed to bring total calcium intake to approximately 1000 mg daily. Subjects who meet all inclusion and exclusion criteria based on labs and history will be scheduled for a baseline visit. Concomitant medications and existing baseline conditions will be collected by interview. Information about the use of prior osteoporosis treatment will be obtained and recent BP use will be categorized for randomization.

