**Baseline Visit:** Baseline visits will be scheduled when all results are in and within one month of fracture. Subjects will be seen in the morning after an overnight fast. Blood will be drawn and subjects will be allowed breakfast. Vitamin D supplements (1000 IU daily) will be provided to help to maintain adequate 25OHD serum levels and calcium intake will be reviewed. A blood sample will be collected at baseline and at every visit to assess calcium level for safety. Blood samples for biochemical indices of bone turnover (serum PINP for bone formation and serum CTX for bone resorption) and 25(OH)D will be obtained at baseline and every month and analyzed by batch at the Helen Hayes Hospital Regional Bone Center. Subjects will complete the lower extremity physical function tests, an Activities of Daily Living (ADLs) and SF-36 physical function survey, NRS for pain and a survey with pill count to determine narcotic use. Subjects will be randomly assigned (with separate schemes for males and females and prior BP use) to receive either TPTD 20 mcg or identically appearing placebo. Only the statistician will be aware of subject assignment and the pharmacist will distribute the appropriate TPTD or placebo medication. Subjects will be taught by the research nurse the method of daily self-administered subcutaneous injection techniques using TPTD or placebo pens, and provided written instructions for drug administration with a diary to track injections. We have extensive experience teaching subjects to administer TPTD with >90% compliance in elderly populations and subjects in the modelling recruitment phase were willing to take TPTD. Treatment will continue for the 3 months of the proposed study. Even if the fracture heals sooner, these subjects all have osteoporosis and should maintain their osteoporosis treatment for the duration of the double blind trial while other outcomes are evaluated (0 to 3 months).

**Retention:** Subjects will be called weekly during the 3 month blinded trial to monitor side effects and adverse events, and to ensure compliance with the protocol, including medication adherence.

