Randomization will be by gender and bisphosphonate (BP) use creating 4 randomly permuted block randomization lists. We will not exclude prior BP use, however, since the recent use of BP may impact TPTD effect, BP use will be used to create the following strata for randomization within males and females: (1) Recent BP use (greater than one year use within 2 years)/female or (2) Recent BP use (greater than one year use within 2 years)/male (3) distant or never ( $\geq 3$  years since last BP or never users)/female (4) distant or never ( $\geq 3$  years since last BP or never users)/male. We hypothesize that acceleration of pelvic fracture healing by TPTD will not be significantly affected by prior BP use because this skeletal site is largely cancellous bone and we believe that TPTD response is less affected by prior BP use in primarily cancellous sites (vs cortical sites). In addition, initial fracture healing is dependent on callus formation which is not diminished by BP. Furthermore, there was no significant difference in delayed union of the fractured bone between placebo and zoledronic acid after hip fracture. However, given the potential for recent BP use to alter BMD and turnover response to TPTD, we will stratify by BP use to ensure that any effect of BP on TPTD is equally distributed between the placebo and TPTD groups. In addition, we will record length and type of bisphosphonate use as a potential covariate in the analysis to evaluate effect modification by prior BP use.

**Open Label Extension:** After 3 months of placebo versus TPTD, when the data for the primary analysis of all aims has been collected, all persons will be offered to continue TPTD (open label) for 9 months while pain and physical performance are assessed and surveys completed every 3 months. The open label protocol will allow

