**Statistical Plan:** There will be no interim analysis and missing outcome data will not be imputed. Statistical analysis will be performed using SAS software (Cary NC). Between group differences at baseline will be compared with t-tests or Wilcoxon rank sum tests and chi-square tests as appropriate (p-value <0.05 for significance). Randomization by the method of randomly permuted blocks will be created for gender and BP use groups. Our primary analysis is ITT analysis and our primary outcome (SA#1) is the categorization of the level of bridging seen on focus CT into the scores from 0 to 4, described above between 0 and 3 months. The difference in cortical bridging will be evaluated by a 2x5 chi-square (group x score) with a trend test (Jonckheere-Terpstra) to see whether TPTD treated "trend" to have more higher bridging scores than the placebo group. We expect 30% - 50% superiority with TPTD at 3 months. This categorical outcome will be further analyzed with generalized estimating equations (GEE) for longitudinal repeated measures assuming a Poisson distribution with weighting from logistic regression analysis of the missingness pattern. Secondary analyses of covariates, sensitivity analyses and the "per protocol" analysis will incorporate the aforementioned approach into this aim's GEE analysis. This analysis addresses the question "Do patients treated with TPTD show more rapid fracture healing than those given placebo? For SA #2, we anticipate that the difference in pain score between the TPTD and placebo groups in the proposed study will be > 30% at each monthly time point (0-3 months). We will use a between-groups linear mixed model for repeated measures (LMMrm) to estimate the primary outcome of the difference in the mean within-subject change from baseline in the two groups at the end of the placebo controlled trial (0-3 months) and again to explore change from 3 to 12 months in the open label extension. In addition, narcotic and non-narcotic pain medication use will enter the model as time-dependent covariates. This analysis addresses the two questions, "Do patients treated with TPTD show more rapid reduction in reported pain level than those not so treated? If so, when?" For SA#3, the CSPPS is the outcome. A linear mixed model for repeated measures (LMMrm) will be used with fixed effects of treatment group (TPTD vs. placebo), time (D1, 4-, 8- and 12-wk) and their interaction, the baseline level of the CSPPS and days from injury to randomization entered as covariates, and a within-subject covariance structure selected by empirical methods prior to hypothesis testing. This plan will be repeated for the "per protocol" analysis in which subjects are limited to those showing 80% or greater compliance over the 12-week trial. This statistical plan addresses the two clinical questions, "Do patients treated with TPTD recover lower limb function faster than those not so treated? If so, when?" LMMrm will be used to analyze data from 3-12 months and assess group by time interaction. We will group on prior BP exposure strata to account for possible heterogeneity in the R-side covariance structure.

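### The primary analysis names no deciding test, sidedness or alpha and leaves out the randomisation factors, and the bisphosphonate randomisation lists do not cover every eligible patient

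*Combined protocol and SAP*

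**What the plan says.** **Randomisation lists.** Section 4, Randomization and Medication, says "We will not exclude prior BP use", and the exclusion criteria contain no BP item. Within each sex there are two lists. For women these are "Recent BP use (greater than one year use within 2 years)/female" and, on the other side, 3 or more "years since last BP or never users)/female"; the male lists use the same limits. The Screening visit text adds that "recent BP use will be categorized for randomization", and the Baseline Visit text says assignment is made "with separate schemes for males and females and prior BP use". Neither adds a definition.

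**Primary test.** The Protocol Summary says "The treatment difference in cortical bridging will be evaluated by a 2x5 chi-square (group x score) with a trend test". The Statistical Plan in section 7 says "The difference in cortical bridging will be evaluated by a 2x5 chi-square (group x score) with a trend test". Both name Jonckheere-Terpstra as the trend test and give its purpose as showing whether TPTD shifts patients toward higher scores. The 0.05 level in the Statistical Plan belongs to the baseline comparisons. The Sample Size Justification uses 1% alpha, 40 per group and 100% v 60% completed healing, and reports more than 95% power from a comparison of proportions.

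**Covariates.** The primary tests carry none. Gender and recent BP use are candidates in the models, screened at p<0.2. BP strata group the residual covariance in the mixed models. On BP history, "we will record length and type of bisphosphonate use as a potential covariate in the analysis to evaluate effect modification by prior BP use". Days from injury to randomisation is a covariate for the physical performance score (CSPPS) but is not on the candidate list.

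**The concern.** Three separate things are at stake.

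- **(a) Lists.** A patient who fits neither BP category cannot be randomised by the written rule. That patient also has no defined value for the BP stratum that the mixed models group on.
- **(b) Deciding test.** Two tests give two p-values, and they respond to different departures from equality. If the deciding test, its direction and its threshold are settled only after unblinding, the conclusion of a 100-patient trial could depend on that choice. The power statement covers neither named test.
- **(c) Adjustment.** Stratifying by sex and BP use implies that these factors may matter, yet the primary test does not use them. Any precision they offer is given up.

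**Working it through.** **(a) The lists.** Let t be years since last BP use and L the length of a single continuous course. The distant or never list takes t ≥ 3 and never users. The recent category has two readings.

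- Reading 1, more than one year of use inside the 2-year window: min(L, 2 − t) > 1, so t < 1 and L > 1.
- Reading 2, a course of more than one year with last use inside the window: L > 1 and t ≤ 2.

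| Patient | Reading 1 | Reading 2 |
|---|---|---|
| L > 1, t < 1 | recent | recent |
| L > 1, 1 ≤ t ≤ 2 | no list | recent |
| any L, 2 < t < 3 | no list | no list |
| L ≤ 1, t < 3 | no list | no list |

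Example: L = 5, t = 1.5 gives 2 − 1.5 = 0.5 years inside the window, so the patient is unplaced on reading 1 and recent on reading 2. The documents do not give BP histories, so the number affected cannot be derived.

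**(b) The plan's own power figure.** With 100% v 60%, 40 per group and two-sided 1%, the pooled proportion is 0.80. The null SE is √(2 × 0.8 × 0.2/40) = 0.0894 and the alternative SE is √(0.6 × 0.4/40) = 0.0775. Then (0.4 − 2.576 × 0.0894)/0.0775 = 2.19, which is 98.6% power. The stated figure of more than 95% reproduces, for two proportions only.

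**The two named tests.** With two arms, Jonckheere-Terpstra is the Wilcoxon rank-sum test. Assume placebo scores 0 to 4 of 10/10/20/30/30% (60% at 3 or 4, matching the plan) and a common odds ratio of 3. Simulated two-sided power:

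| Per arm, alpha | Trend | Chi-square |
|---|---|---|
| 40, 5% | 75% | 52% |
| 50, 5% | 84% | 63% |
| 40, 1% | 51% | 26% |

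At 40 per arm and 5% the tests disagree in about 27% of trials. Sidedness matters too: with a similar assumed placebo distribution (12/14/14/30/30%), the trend test has 75% power two-sided and 84% one-sided at 5%.

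Now take the planned effect: all TPTD patients at score 3 or 4, split 50/50, 40 per arm, 1% alpha. The plan gives no split between scores 3 and 4, so the placebo split is varied, with scores 0 to 2 held at 10/10/20%:

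| Placebo at scores 3/4 | Trend | Chi-square |
|---|---|---|
| 40/20% | 97% | 97% |
| 30/30% | 80% | about 95% |
| 20/40% | 48% | about 98% |

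The trend test loses power as healed placebo patients hold relatively more 4s. In the last row 40/60 = 67% of them score 4, against 50% of TPTD patients. With placebo 30/30 and TPTD 30/70, both tests have about 98%. If completed healing means score 4 alone, both reach 100%.

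**(c) Adjustment.** Simulated with 100 patients, four lists, blocks of 4, 25% men (the plan's figure for pelvic fractures), 20% recent BP use (assumed) and 5% alpha, comparing rank ANCOVA with the plain trend test:

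- no prognostic effect: gain of 0.1 to 0.2 points;
- assumed log-odds of +0.5 for sex and −0.5 for BP: gain of 0.5 to 1.4 points;
- an added days effect (assumed odds ratio 2 per 10 days, start day spread over 0 to 30): 41.0% to 45.4% at treatment odds ratio 2, and 77.9% to 82.5% at 3;
- the planned 100% v 60%: no gain.

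Null rejection at nominal 5% was 4.9 to 5.2% for the plain test and 5.2 to 5.3% for rank ANCOVA. For the proportional-odds model it was 5.5 to 5.9% (score test) and 5.8 to 6.0% (likelihood-ratio test). The simulation SE for the last two is about √(0.05 × 0.95/10,000) = 0.2 points. The recent-BP male list would hold about 100 × 0.25 × (0.10 to 0.30, assumed) = 2.5 to 7.5 patients.

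**The case against.** **The trend test is already the intended one.** Both statements of the primary analysis attach their purpose to it. That lean is real, but it does not settle sidedness, or whether 1% or 5% applies.

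**A reader might infer that two tests mean an inflated false-positive rate.** The documents do not support this. Inflation would need a rule that success on either test counts, and no section gives one.

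**The reversal argues against a rank test.** At the planned effect it can be the weaker test. This stands as a reason to restate power. It does not change which test fits the question: the plan asks about a shift toward higher scores, whereas the chi-square ignores the order of the scores. The reversal also rests on assumed splits in both arms and is absent under some of them.

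**Forty per arm may be too few.** The Protocol Summary codes missing endpoints in an intention-to-treat analysis, so 50 per arm is the nearer case. There the 80% in the 30/30 row becomes about 89%. This stands, and both sizes should be shown.

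**The list gap is minor.** BP length and type are recorded, so patients can be coded later once a rule exists, and no section says that sites assign the list themselves. Both points are fair. A reader might infer biased allocation, but assignment remains randomised and blinded.

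**Adjustment is a preference.** A reader might infer that the unadjusted test is invalid because it ignores the strata; it is valid. The plan allows covariate analyses in secondary models, baseline imbalances at p<0.20 can bring in days from injury, and days is not a stratification factor. The plan also expects little effect of BP use on healing. So this part is an improvement, not an error.

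**Conclusion.** The concern holds in three parts of unequal weight.

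- **(a) Wrong as written.** The BP categories leave eligible patients without a list on either reading, and recent use is ambiguous for longer courses that ended 1 to 2 years ago. The gap is operational and its size unknown.
- **(b) The substantive part.** No section states the deciding test, its sidedness or its alpha. The only alpha tied to this outcome belongs to a two-proportion calculation that is not the planned analysis. The gap in power between the named tests is 23 points at 40 per arm (75 − 52) and 21 at 50 (84 − 63) under the assumed odds ratio of 3. At the planned effect, trend power ranges from 48% to 97% over the placebo splits examined. All of these rest on assumed score distributions.
- **(c) A free improvement.** The gain is about 0.5 to 1.4 points for modest sex and BP effects, and up to about 4 to 5 with a strong days effect, all under assumed prognostic strengths. There is none at the planned effect.

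These should be settled before unblinding. They do not undermine the design.

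**What to change.** 1. Rewrite the BP categories so that every eligible patient falls in exactly one and the recent category has one reading; the sponsor chooses the cut. If enrolment has begun, record the list used for each affected patient and fix the rule before unblinding.
2. Before unblinding, name one two-sided ordinal rank test as the sole primary decision test, state its alpha, and report the chi-square as descriptive.
3. Restate power for that test on the five-level score, over a range of splits between scores 3 and 4 in both arms, for 40 and 50 per arm.
4. Adjust the primary rank test for sex and BP stratum as main effects, for example by rank ANCOVA; main effects suit the sparse recent-BP male list. Enter both as pre-specified fixed effects in the GEE and mixed models instead of screening at p<0.2. Days from injury may be added as an option. Do not substitute a proportional-odds test without a small-sample correction.

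The cost is SAP wording, one rerun of the power calculation and one line in the randomisation specification. The variables are already collected, and no patients or visits are added.

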## **5. Safety:**

Total serum calcium will be assessed at baseline for study eligibility and then at every visit via standard automated chemistry. Avoiding excessive calcium supplements will help prevent hypercalcemia, therefore we will assess diet and use supplementation only to obtain a total intake of 1000 mg daily. Serum calcium will be reviewed by our safety officer ([name] at HSS). A preplanned algorithm for hypercalcemia (defined as >10.1 mg/dl, the upper limit for our laboratory) requires stopping calcium supplements or reducing dietary intake and repeating the measurement within 2 weeks. If hypercalcemia persists, TPTD/placebo will be withheld. At each monthly visit and during the weekly phone calls while on TPTD/Placebo, adverse events (AEs) or serious adverse events (SAEs), comorbidities and concomitant medication use will be recorded by the nurse and reviewed with the site MD (RN and MD are blinded to treatment). Follow-up for any SAE will occur until it is resolved. All SAEs will be reported to the internal safety officer ([name]) and to the DSMB safety officer and NIAMS (through KAI) within 48 hours of the investigator becoming aware of the SAE. The IRB and FDA (IND 126129; [name]) will be notified of SAEs as per their guidelines. The radiographic evaluations will expose subjects to radiation, however this will not exceed normal clinical care and in fact we worked to reduce exposure using our protocol for focus CT imaging. [name] will serve as the internal safety officer for this study and will review all AE, SAEs and serum calcium for safety. In addition, there is a 3 person DSMB for this study that was appointed by NIAMS. The DSMB will receive reports from the study team every six months for additional safety review. Annual reports will also be filed with the FDA, IRB and NIH.

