**Monitoring of Hypercalcemia:** The major safety evaluation of this study is a check for hypercalcemia which will first be assessed at 4 weeks after starting TPTD when calcium levels are found to peak. The development of hypercalcemia may be dependent on an individual's baseline serum calcium level and calcium supplement exposure. Therefore, volunteers will be counseled by the Research Nurse about optimizing dietary calcium intake, and avoiding calcium supplement use in order to prevent the development of hypercalcemia. Calcium supplements will be used only as needed to bring daily calcium intake to 1000 mg a day. Serum calcium levels will be checked at every visit, which occur monthly for the first 3 months after TPTD or placebo initiation and then, during the open label with teriparatide treatment, levels will be checked every three months. Subjects will be advised not to take the TPTD or placebo prior to the blood sample being collected (levels will be obtained at least 16 hours after the last TPTD dose). Serum samples will be analyzed within 24 hours of sample procurement and will be reviewed by the Safety Officer [name] within 24 hours of receipt of result.

If the serum calcium is above 11.5 mg/dl, calcium supplements or dietary calcium will be reduced and the level will be checked again within 3 days. If the level remains >11.5 mg/dl; TPTD will be given on alternate days.

If the serum calcium is between 10.5 and 11.5 mg/dl, calcium supplements or dietary calcium will be reduced and the level will be checked again within 10 days. If serum calcium levels are persistently above 10.5 mg/dl, volunteers will be advised to take TPTD every other day.

In multiple prior trials involving TPTD treatment in hundreds of patients, we have never been required to reduce the dose of TPTD due to hypercalcemia.

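### For blinded-phase calcium that stays above 10.5 mg/dl, section 5 withholds TPTD/placebo, section 6 continues TPTD every other day, and nothing says which governs

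*Combined protocol and SAP*

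**What the plan says.** Section 5 (Safety) of the combined protocol and SAP sets out one rule: "A preplanned algorithm for hypercalcemia (defined as >10.1 mg/dl, the upper limit for our laboratory"). The rule "requires stopping calcium supplements or reducing dietary intake and repeating the measurement within 2 weeks". It ends with the drug action: "If hypercalcemia persists, TPTD/placebo will be withheld".

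Section 6 (Data and Safety Monitoring Responsibilities), under Monitoring of Hypercalcemia, sets out another rule in two bands.

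- Above 11.5 mg/dl: calcium intake is reduced and "the level will be checked again within 3 days". Then: "If the level remains >11.5 mg/dl; TPTD will be given on alternate days".
- From 10.5 to 11.5 mg/dl: calcium intake is reduced and "the level will be checked again within 10 days". Then: "If serum calcium levels are persistently above 10.5 mg/dl, volunteers will be advised to take TPTD every other day".

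Section 6 describes the study's main safety evaluation as "a check for hypercalcemia which will first be assessed at 4 weeks after starting TPTD when calcium levels are found to peak". Its monitoring schedule covers the monthly visits in the first 3 months, on TPTD or placebo, and then the open-label period. It contains no calcium level at which drug is stopped.

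**The concern.** A patient in the blinded phase whose calcium stays above 10.5 mg/dl after calcium intake is reduced meets the condition of both rules. Section 5 takes the patient off drug; section 6 keeps the patient on it at a reduced frequency, even if the level remains above 11.5 mg/dl. The person acting on the result therefore has two incompatible instructions on what section 6 itself treats as the principal safety check. Two patients with the same result could be handled differently, with each decision defensible from the protocol. This is a patient-safety matter first; the effect on the efficacy analysis is secondary.

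**Working it through.** The plan gives no figure to reproduce. The check is a comparison of the two rules.

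**Step 1: do both rules reach the same patient?** Section 5 triggers above 10.1 mg/dl and section 6 above 10.5 or above 11.5. Since 11.5 > 10.5 > 10.1, any patient who meets a section 6 dosing trigger also meets section 5's definition.

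**Step 2: do both rules cover the same phase?** Section 5's action names both TPTD and placebo. Section 6's first check is at 4 weeks, and its schedule includes the monthly visits of the placebo-controlled period. Both cover the blinded phase.

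**Step 3: compare the drug actions.**

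| Calcium still, on recheck | Section 5 | Section 6 | Both possible? |
|---|---|---|---|
| above 10.1, below 10.5 | withhold | no instruction | only section 5 gives an action |
| above 10.5, up to 11.5 | withhold | every other day | no |
| above 11.5 | withhold | alternate days | no |

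A patient can also move between bands. With 10.8 at first and 10.3 on recheck, section 5 withholds, while section 6's trigger for reduced dosing is not met and it gives no other instruction. That is a gap in section 6, not a second pair of opposing instructions.

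**Step 4: compare the recheck times.** All are upper limits.

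| First value | Section 5 limit | Section 6 limit | Time that meets every stated limit |
|---|---|---|---|
| above 10.1, below 10.5 | 14 days | none | 14 days |
| 10.5 to 11.5 | 14 days | 10 days | 10 days |
| above 11.5 | 14 days | 3 days | 3 days |

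Since 3 < 14 and 10 < 14, a recheck on section 6's schedule also satisfies section 5. There is no conflict here.

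**Step 5: is there a rule of precedence?** None was found. Neither section refers to the other's algorithm, calls itself a summary of it, or describes alternate-day dosing as a step before withholding.

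**Step 6: can the difference be counted in doses?** That needs the day of the recheck and the length of the drug action. The recheck has only an upper limit, and neither section says how long withholding or alternate-day dosing lasts. A dose count would be set by the assumptions put in.

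**The case against.** The best argument for the plan is that section 6's two dosing sentences say TPTD alone, although the paragraph before them names placebo where both are meant. On that reading they might not govern blinded treatment. The wording is as described, but the reading fails in practice. The monitoring covers the first 3 months on TPTD or placebo, and section 5 states that the nurse and site physician are blinded, so they could not apply the rule to the active arm only.

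A second argument is that withholding might mean a short hold followed by alternate-day dosing. The text does not exclude this, but nothing says it.

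A third is that little is at stake, and much of this stands. The exclusion criteria remove active hypercalcaemia and current hyperparathyroidism, calcium at screening may not exceed the laboratory's normal, and total calcium intake is held to about 1000 mg a day. One safety officer reviews calcium results within 24 hours of receipt, which limits divergence between sites. Section 6 reports that the team's earlier trials never needed a dose reduction for hypercalcaemia. Low frequency reduces the expected harm; it does not tell the safety officer which instruction to follow.

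A reader might also infer that the recheck times conflict, or that section 5 is in one respect the laxer rule because it allows 2 weeks. Step 4 shows otherwise: these are upper limits and can all be met together.

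**Conclusion.** The contradiction is real and is wrong as written. It is confined to one thing: the drug action when blinded-phase calcium stays above 10.5 mg/dl after calcium intake is reduced. It should be fixed, and the remedy is cheap.

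The conclusion assumes that persistence in section 5 means a repeat value still above its 10.1 mg/dl definition, and that section 6's dosing sentences apply to blinded patients for the reasons given above.

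Two larger claims are tempting, and the documents do not support them.

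- **A stated number of doses lost or gained under one rule against the other.** Without a recheck day or a duration, no such number can be defended. The documents also give no frequency of values above 10.5 mg/dl in this population.
- **Damage to the primary analysis.** It is by intention to treat, so a patient whose drug is withheld or reduced stays in the analysis. The Protocol Summary's coding of a patient as not healed after an adverse event applies only when the endpoint assessment is missing through drop-out or loss to follow-up; a drug hold does not by itself cause that.

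**What to change.** Use one algorithm, worded for TPTD/placebo, in both sections:

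- Calcium above 10.1 and below 10.5 mg/dl: stop supplements or reduce dietary calcium, and recheck within 2 weeks.
- Calcium from 10.5 to 11.5 mg/dl: the same, with a recheck within 10 days.
- Calcium above 11.5 mg/dl: the same, with a recheck within 3 days.
- If the recheck is still above 10.1 mg/dl: withhold TPTD/placebo.

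Delete section 6's two alternate-day sentences for hypercalcaemia. Its separate every-other-day provision for troublesome side effects can stay. State that the algorithm also covers open-label TPTD, because section 6's monitoring extends into that period.

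Every threshold, recheck time and action here is already in one of the two sections. Withholding against reducing the dose is a clinical choice. If the sponsor and safety officer want alternate-day dosing as a step before withholding, the text should give the calcium band in which it applies and the value at which drug is withheld. Neither section says when normal dosing resumes; the same amendment is a convenient place to settle that, but the choice is theirs.

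The cost is a protocol wording amendment, with no added patients or scheduled visits. The downside is that a few patients may miss some doses.
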